#### Diluent and Sham Product

1X SPG (7.4% sucrose, 3.8 mM KH2PO4, 7.2 mM K2HPO4, 5.4 mM L-glutamic acid). Each vial has a fill volume of 1.2 mL. The diluent will also be used as a sham inoculum. Each vial was individually labeled with the product name, description, and caution statement. The label was affixed to 2 mL cryogenic vials prior to final fill with 1X SPG [Charles River Laboratories, Malvern PA] (Lot #141701).

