3.2.3. Infection Status

Infection status, independent of symptom status, will be defined at the participant level in two different ways:

- Participants are considered **Infected** if viral shedding is detected in NP swab(s) by qualitative and/or quantitative RT-PCR on at least two days beginning 24 hours after challenge until Study Day 8
- Participants are considered to be **Currently Infected** from their first through their last study days meeting the viral shedding definition above (and in [Section 3.2.2](#)), regardless of any intermittent negative results between those two study days.

Pre-infection and post-infection results will be determined based on the definition of Current Infection above. New-onset symptoms will be those with a maximum severity post-infection (starting on the day of first RT-PCR positivity) above that of baseline, for infected participants.

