4. INVESTIGATIONAL PLAN

4.1. Overall Study Design and Plan

This is an exploratory Phase 1, blinded, randomized, dose-finding influenza virus challenge study in approximately between 62-114 (targeted maximum sample size of 106 active challenge virus plus 8 shams) males and non-pregnant females, 18 to 45 years old, inclusive, who are in good health and meet all eligibility criteria. The clinical study is designed to determine the optimal infectious dose and safety profile of a recombinant influenza A/Texas/71/2017 (H3N2) clade 3C3a strain in healthy adult volunteers.

Potentially eligible study participants may be pre-screened under an active screening protocol (DMID 20-0004) to identify those with HAI antibody titers $\leq 1:40$ specific to the challenge virus strain. During the study screening period of this protocol (Day -45 to Day -3), participants who have not received a seasonal influenza vaccine within the past 4 months and for whom there are no safety concerns from standard safety assessments and screening labs are eligible for enrollment to the study.

Safety assessments and safety labs include a medical history review, physical examination, ECG, a chest X-ray (CXR), HIV and hepatitis B/C testing, baseline SpO₂ saturation, and testing for WBCs, ALC, hemoglobin, platelets, ALT, and creatinine. Women of childbearing potential must have a negative serum pregnancy test at screening and a negative urine pregnancy test on Day -2. Likewise, participants must have a negative drug urine toxicology test (unless the drug is deemed acceptable by the Investigator), negative multiplex respiratory viral test, and a negative SARS-CoV-2 RT-PCR test at screening and on Day -2. After a standard physical exam to exclude active infection or other illness, participants began confinement on Day -2 and remain confined for up to 12 days (Days -2 to 10).

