5.3.2. Intent-to-Treat (ITT) Population

The Intent-to-Treat population will consist of all enrolled participants.

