8. IMMUNOLOGICAL EVALUATION

8.1. Secondary Immunogenicity Analyses

Only secondary immunogenicity analysis of HAI, MN, NAI, and anti-HA stalk assay data will be included in the interim CSR. Exploratory immunogenicity analysis not included in this SAP will be planned in a separate SAP addendum to this analysis plan and presented in an addendum to the CSR or one or more separate reports for the purposes of manuscript development.

Immunogenicity analyses are planned in the ITT population. If 10% or more of the timepoints utilized in the immunogenicity analyses would be excluded by the list given in [Section 5.3.3](#) to define the Per Protocol population, the secondary immunogenicity analyses will be conducted in the PP population as a sensitivity analysis.

HAI, MN, and anti-HA stalk antibody titers against the challenge strain will be analyzed by time point, challenge dose group, and infection status in [Table 49](#), [Table 50](#), and [Table 52](#), respectively. Geometric mean titers (GMTs) will be computed at each time point for each group, as well as geometric mean fold-rise (GMFR) and seroconversion (as defined in [Section 3.2.7](#)) at each post-challenge time point. Associated 95% CIs will be presented as well. GMTs and 95% CIs will be presented graphically in [Figure 16](#) and [Figure 18](#), and the entire distribution of titers reported at each visit will be presented in reverse cumulative distribution (RCD) curves in [Figure 19](#), [Figure 20](#), and [Figure 22](#).

The assays will be analyzed similarly by symptomatic infection status in [Table 53](#), [Table 54](#), and [Table 56](#).

Antibody titers will be listed, by assay, in [Listing 11](#).

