Notes: N = Number of participants in the Safety population reporting symptoms relevant to the given subgroup; n = Number of participants reporting each symptom, regardless of timing with respect to RT-PCR positivity. Uninfected participants include all those RT-PCR+ on no more than one study day.

^aAs reported on the Modified Jackson Score (MJS) tool; maximum severity across the challenge period reported.

^bAs part of vital signs assessments, with temperature collected three times daily during the challenge period. Fever and feverishness (from MJS) contribute as one item towards the Modified Jackson Score.

^cAs part of clinical safety laboratory assessments, on Study Days 2, 4, 8, and any supplemental visits during the challenge period.

Table 27: Paired Comparisons of Influenza Symptoms Reported Before, During, and After Infection, Infected Participants in the Safety Population

Symptom	Severity	Pre-Infection	Current Infection	Post-Infection	Pre-Infection vs. Current Infection	Pre-Infection vs. Post-Infection	Current Infection vs. Post-Infection
		n (%)	n (%)	n (%)	p-value ^d	p-value ^d	p-value ^d
Any Symptom	None	x (x.x)	x (x.x)	x (x.x)	0.xx	0.xx	0.xx
	Mild or Just Noticeable	x (x.x)	x (x.x)	x (x.x)	-	-	-
	Moderate or Bothersome from Time to Time	x (x.x)	x (x.x)	x (x.x)	-	-	-
	Severe or Bothersome Most or All of the Time	x (x.x)	x (x.x)	x (x.x)	-	-	-
Runny Nose ^a	0: None	x (x.x)	x (x.x)	x (x.x)	0.xx	0.xx	0.xx
	1: Just Noticeable	x (x.x)	x (x.x)	x (x.x)	-	-	-
	2: Bothersome from Time to Time	x (x.x)	x (x.x)	x (x.x)	-	-	-
	3: Bothersome Most or All of the Time	x (x.x)	x (x.x)	x (x.x)	-	-	-
Stuffy Nose ^a	0: None	x (x.x)	x (x.x)	x (x.x)	0.xx	0.xx	0.xx
	1: Just Noticeable	x (x.x)	x (x.x)	x (x.x)	-	-	-
	2: Bothersome from Time to Time	x (x.x)	x (x.x)	x (x.x)	-	-	-
	3: Bothersome Most or All of the Time	x (x.x)	x (x.x)	x (x.x)	-	-	-
Sneezing ^a	0: None	x (x.x)	x (x.x)	x (x.x)	0.xx	0.xx	0.xx
	1: Just Noticeable	x (x.x)	x (x.x)	x (x.x)	-	-	-
	2: Bothersome from Time to Time	x (x.x)	x (x.x)	x (x.x)	-	-	-
	3: Bothersome Most or All of the Time	x (x.x)	x (x.x)	x (x.x)	-	-	-
Sore Throat ^a	0: None	x (x.x)	x (x.x)	x (x.x)	0.xx	0.xx	0.xx
	1: Just Noticeable	x (x.x)	x (x.x)	x (x.x)	-	-	-

Symptom	Severity	Pre-Infection	Current Infection	Post-Infection	Pre-Infection vs. Current Infection	Pre-Infection vs. Post-Infection	Current Infection vs. Post-Infection
		n (%)	n (%)	n (%)	p-value ^d	p-value ^d	p-value ^d

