Notes: n = Number of participants in the Intent-to-Treat population with available results; GMT = Geometric Mean Titer; GMFR = Geometric Mean Fold-Rise.

^a RT-PCR+ results reported on at least two days during the challenge period (Days 2 to 8).

^b Confidence Interval calculated based on the Student's t-distribution.

^c Exact binomial confidence interval calculated using the Clopper-Pearson methodology.

Similar Tables:

Table 50: Summary of Microneutralization Antibody Titers Against A/Texas/71/2017 (H3N2), clade 3C3a Virus, by Challenge Dose Group, Infection Status, and Study Day, ITT Population*

Table 51: Summary of Neuraminidase Inhibition Antibody Titers Against A/Texas/71/2017 (H3N2), clade 3C3a Virus, by Challenge Dose Group, Infection Status, and Study Day, ITT Population

Table 52: Summary of Anti-Hemagglutination Stalk Antibody Titers Against A/Texas/71/2017 (H3N2), clade 3C3a Virus, by Challenge Dose Group, Infection Status, and Study Day, ITT Population*

Table 53: Summary of Hemagglutination Inhibition Antibody Titers Against A/Texas/71/2017 (H3N2), clade 3C3a Virus, by Symptomatic Infection Status, and Study Day, ITT Population

Study Day	Statistic	Symptomatic and Infected (N=X)	Asymptomatic and Infected (N=X)	Symptomatic and Uninfected (N=X)	Asymptomatic and Uninfected (N=X)
Baseline	n	x	x	x	x
	GMT (95% CI) ^b	x.x (x.x, x.x)	x.x (x.x, x.x)	x.x (x.x, x.x)	x.x (x.x, x.x)
Day 8	n	x	x	x	x
	GMT (95% CI)	x.x (x.x, x.x)	x.x (x.x, x.x)	x.x (x.x, x.x)	x.x (x.x, x.x)
	GMFR (95% CI) ^b	x.x (x.x, x.x)	x.x (x.x, x.x)	x.x (x.x, x.x)	x.x (x.x, x.x)
	Seroconversion - % (95% CI) ^c	x.x (x.x, x.x)	x.x (x.x, x.x)	x.x (x.x, x.x)	x.x (x.x, x.x)
Day 15	n	x	x	x	x
	GMT (95% CI)	x.x (x.x, x.x)	x.x (x.x, x.x)	x.x (x.x, x.x)	x.x (x.x, x.x)
	GMFR (95% CI)	x.x (x.x, x.x)	x.x (x.x, x.x)	x.x (x.x, x.x)	x.x (x.x, x.x)
	Seroconversion - % (95% CI)	x.x (x.x, x.x)	x.x (x.x, x.x)	x.x (x.x, x.x)	x.x (x.x, x.x)
Day 29	n	x	x	x	x
	GMT (95% CI)	x.x (x.x, x.x)	x.x (x.x, x.x)	x.x (x.x, x.x)	x.x (x.x, x.x)
	GMFR (95% CI)	x.x (x.x, x.x)	x.x (x.x, x.x)	x.x (x.x, x.x)	x.x (x.x, x.x)
	Seroconversion - % (95% CI)	x.x (x.x, x.x)	x.x (x.x, x.x)	x.x (x.x, x.x)	x.x (x.x, x.x)
Day 57	n	x	x	x	x
	GMT (95% CI)	x.x (x.x, x.x)	x.x (x.x, x.x)	x.x (x.x, x.x)	x.x (x.x, x.x)
	GMFR (95% CI)	x.x (x.x, x.x)	x.x (x.x, x.x)	x.x (x.x, x.x)	x.x (x.x, x.x)
	Seroconversion % (95% CI)	x.x (x.x, x.x)	x.x (x.x, x.x)	x.x (x.x, x.x)	x.x (x.x, x.x)

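### Tables 53-56 pool sham recipients with virus recipients in the two Uninfected antibody columns

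*SAP*

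**What the plan says.** SAP 8.1 introduces Tables 53, 54 and 56 in one sentence, "The assays will be analyzed similarly by symptomatic infection status in" those tables, and SAP 8.2 adds Table 55 for NAI. The table titles end "by Symptomatic Infection Status, and Study Day, ITT Population". The shell for Table 53 has four columns: symptomatic and infected, asymptomatic and infected, symptomatic and uninfected, and "Asymptomatic and Uninfected (N=X". Tables 54-56 follow the same shell. No footnote or instruction mentions sham.

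SAP 5.3.2 states: "The Intent-to-Treat population will consist of all enrolled participants". Under SAP 3.2.3 a participant is infected "if viral shedding is detected in NP swab(s) by qualitative and/or quantitative RT-PCR on at least two days beginning 24 hours after challenge". The note to Table 26 gives the complement: "Uninfected participants include all those RT-PCR+ on no more than one study day". Neither rule refers to the assigned arm. Protocol 6.2.2 says of the SPG diluent: "The diluent will also be used as a sham inoculum".

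Elsewhere the plan keeps sham apart. Protocol 9.5.1 says that summaries will generally be by dose group, with sham recipients from all cohorts forming one group. Tables 49-52 report the same four assays by dose group and infection status with a sham column. Table 16 has a column for any active dose beside a sham column, and Table 60 has a column for all recipients of active virus.

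**The concern.** The two Uninfected columns mix two kinds of participant. One received live virus but did not reach two RT-PCR positive days. The other received no virus. Antibody rise in the first group is informative, because a virus recipient with no or one positive day who seroconverts may have had an infection that the shedding rule did not capture. Sham recipients had no challenge exposure, and averaging them in pulls seroconversion and GMFR toward no response.

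The mixture also depends on how the trial escalated, since both the number of shams and the number of uninfected virus recipients change with the path. The same response among exposed participants could therefore be displayed differently after a different path. The symptomatic and uninfected column is likely to be small, and sham recipients with background symptoms would fall in it.

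**Working it through.** **1. Reproduce the plan's counts.** Protocol 9.3.2 gives 12 active plus 1 sham per cohort at the two lower doses (up to three cohorts each) and 17 plus 1 at the highest (two cohorts).

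- Active maximum: 3×12 + 3×12 + 2×17 = 106. Sham maximum: 3 + 3 + 2 = 8. Total 114. This matches SAP 4.1, "targeted maximum sample size of 106 active challenge virus plus 8 shams".
- Path 1A, 2A, 3A, 3B: 12 + 12 + 17 + 17 = 58 active and 4 sham, total 62. This is the lower figure in SAP 4.1.
- 10^4 confirmed through 1A, 1B, 1C: 36 active and 3 sham, total 39.

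**2. Place the sham recipients.** ITT covers everyone enrolled. Protocol 9.4 words ITT differently, as subjects who received the study challenge, but the SAP's own ITT tables (for example Table 49) carry a sham column, so sham is in. A sham recipient without two positive days can only enter one of the two Uninfected columns.

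**3. Sham share of the two Uninfected columns combined.** With S sham, A active and infection rate q among active recipients, and all sham recipients uninfected:

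w = S / [S + A(1−q)]

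The documents do not give q. The range 50%-80% is an assumption, chosen in view of the 55%-80% attack rate targeted in SAP section 2.

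| Assumed q | 58 + 4: uninfected active | w | 106 + 8: uninfected active | w |
|---|---|---|---|---|
| 50% | 29.0 | 12.1% | 53.0 | 13.1% |
| 60% | 23.2 | 14.7% | 42.4 | 15.9% |
| 70% | 17.4 | 18.7% | 31.8 | 20.1% |
| 80% | 11.6 | 25.6% | 21.2 | 27.4% |

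**4. Effect on the estimates.** Let p and g be the seroconversion rate and GMFR among uninfected virus recipients, and let sham recipients show no rise. Across the two columns combined, seroconversion becomes (1−w)p and GMFR becomes g^(1−w), so log GMFR shrinks by the fraction w. With illustrative p = 30% and g = 2.0 at 106 + 8:

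- q = 60%: 30% × 0.841 = 25.2%, and 2.0^0.841 = 1.79.
- q = 80%: 30% × 0.726 = 21.8%, and 2.0^0.726 = 1.65.

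**5. If 10^4 is confirmed.** Protocol 4.1 requires at least 80% cases over the three cohorts. Every case is infected, so uninfected virus recipients cannot outnumber the non-cases among them.

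- Active-only denominator: 0.80 × 36 = 28.8, so at least 29 cases and at most 36 − 29 = 7 uninfected active. w is at least 3/(3+7) = 30%.
- All participants, as SAP 4.1 states for the escalation attack rate: 0.80 × 39 = 31.2, so at least 32 cases. If no sham is a case, at most 36 − 32 = 4 active are uninfected, and w is at least 3/(3+4) = 43%.

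Both bounds use the targeted cohort sizes and take all three shams as uninfected.

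**6. Each column separately.** In column j the share is s_j/(s_j + a_j), where s_j and a_j are its sham and active counts. These depend on symptom rates among sham and uninfected virus recipients, which the documents do not give. If all shams fell in one column, that column would be diluted by more than w and the other not at all.

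**The case against.** The strongest reply is that the plan already reports most of this. Tables 49-52 give n, GMT, GMFR and seroconversion for uninfected participants in each dose group, with sham separate. Pooled seroconversion among uninfected virus recipients is the n-weighted mean of the printed percentages, and pooled GMFR is the n-weighted geometric mean, up to rounding and missing pairs. Figures 16-22 keep the four challenge groups as separate lines, and Listing 11 gives individual titers. A reader might infer that the response of exposed but uninfected participants appears nowhere. That inference fails. What is missing is the split of that response by symptom status.

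Four other stronger readings also go too far.

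- A reader might expect one printed uninfected rate to fall by the share w. Table 53 prints no combined Uninfected column, so w describes the two columns together.
- A reader might take the Uninfected columns to be RT-PCR negative. They include participants with one positive day.
- A reader might treat these tables as the SAP's test of the two-day rule. The SAP varies that rule in Table 14 (at least one day, at least three days). The stated objective for serology is to describe responses, and no test or decision rests on Tables 53-56.
- A reader might take it as given that sham recipients cannot respond. This is an assumption. The shells allow for an infected sham recipient, who would enter an Infected column.

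It is also fair that grouping by clinical outcome is planned (SAP 5.1), that Tables 20, 26 and 45 also lack a sham column, and that an uninfected sham recipient is correctly labelled. The shift is small against sampling error: 4/17 = 23.5% has an exact 95% interval of 6.8%-49.9%, and 4/21 = 19.0% has 5.4%-41.9%. If 10^4 is confirmed on the all-participant rule, a rate based on at most four virus recipients says little either way.

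These points limit the consequence. They do not explain why unexposed participants should be averaged into these columns when the plan separates them elsewhere.

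**Conclusion.** The concern holds in a limited form. As laid out, Tables 53-56 pool sham recipients with virus recipients who were RT-PCR positive on fewer than two days, so the Uninfected columns do not describe exposed participants. This follows from the ITT definition and the column layout; no sentence states it as an intention.

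The relative shrinkage of seroconversion and log GMFR over the two columns combined is about 12%-27% for assumed infection rates of 50%-80%, and at least 30% or 43% if 10^4 is confirmed, depending on the denominator. It rests on sham recipients being uninfected and showing no rise, and on exposed but uninfected participants showing some. If the latter show none, there is nothing to dilute. Only the symptom breakdown among virus recipients is affected, in descriptive tables without the topline asterisk. This is a minor but free improvement.

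**What to change.** Restrict the four columns of Tables 53-56 to participants who received challenge virus, and say so in the titles and footnotes. Show sham as a separate fifth column, or refer the reader to the sham column in Tables 49-52. SAP 8.1 and 8.2 need one matching sentence each. The cost is a subsetting condition and at most one extra column. No new data are needed and no other analysis changes.

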14.3 Safety Data

14.3.1 Displays of Adverse Events

Table 57: Overall Summary of Adverse Events*

Participants ^a with	10 ⁴ TCID ₅₀ Challenge Virus (N=X)		10 ⁵ TCID ₅₀ Challenge Virus (N=X)		10 ⁶ TCID ₅₀ Challenge Virus (N=X)		Sham Inoculum (N=X)		All Participants (N=X)	
	n	%	n	%	n	%	n	%	n	%
At least one unsolicited adverse event	x	x.x	x	x.x	x	x.x	x	x.x	x	x.x
At least one related unsolicited adverse event	x	x.x	x	x.x	x	x.x	x	x.x	x	x.x
Mild (Grade 1)	x	x.x	x	x.x	x	x.x	x	x.x	x	x.x
Moderate (Grade 2)	x	x.x	x	x.x	x	x.x	x	x.x	x	x.x
Severe (Grade 3)	x	x.x	x	x.x	x	x.x	x	x.x	x	x.x
At least one severe (Grade 3) unsolicited adverse event	x	x.x	x	x.x	x	x.x	x	x.x	x	x.x
Related	x	x.x	x	x.x	x	x.x	x	x.x	x	x.x
Unrelated	x	x.x	x	x.x	x	x.x	x	x.x	x	x.x
At least one serious adverse event ^b	x	x.x	x	x.x	x	x.x	x	x.x	x	x.x
At least one related, serious adverse event	x	x.x	x	x.x	x	x.x	x	x.x	x	x.x
At least one adverse event leading to early termination ^c	x	x.x	x	x.x	x	x.x	x	x.x	x	x.x

N = Number of participants in the Safety population; n = Number of participants meeting the given criterion.

^a Participants are counted once for each category regardless of the number of events.

^b A listing of Serious Adverse Events is included in [Table 61](#).

^c As reported on the Adverse Event eCRF.

Table 58: Adverse Events Occurring in 5% of Participants in Any Study Group by MedDRA System Organ Class and Preferred Term, and Study Group - Safety Population*[Implementation Note: This table should include a row for any PT/SOC reported by $\geq 5\%$ participants in any group.]

MedDRA System Organ Class	Preferred Term	10^4 TCID ₅₀ Challenge Virus (N=X)		10^5 TCID ₅₀ Challenge Virus (N=X)		10^6 TCID ₅₀ Challenge Virus (N=X)		Sham Inoculum (N=X)		All Participants (N=X)	
		n (%)	# Events	n (%)	# Events	n (%)	# Events	n (%)	# Events	n (%)	# Events
SOC1	PT1										
Etc.	Etc.										

Notes: N = Number of participants in the Safety population (number of participants at risk); n= number of participants reporting event.

14.3.1.1 Unsolicited Adverse Events**Table 59: Summary of Unsolicited Adverse Events by MedDRA System Organ Class and Preferred Term, Time Post-Challenge, and Challenge Dose Group***

[Implementation note: If any unsolicited AEs are reported during supplemental challenge period visits (e.g., Visits 08S, 08T, etc.), include in the Day 1-8 portion of the table and add a footnote to clarify how many AEs of that nature occurred.]

MedDRA System Organ Class	MedDRA Preferred Term	Day 1-8 (Challenge Period)				Day 9+ (Post-Discharge)				Any Time Post-Challenge			
		n	%	95% CI	# Events	n	%	95% CI	# Events	n	%	95% CI	# Events
10^4 TCID₅₀ Challenge Virus (N=X)													
Any SOC	Any PT	x	x.x	x.x, x.x	x	x	x.x	x.x, x.x	x	x	x.x	xx, xx	x
[SOC 1]	Any PT	x	x.x	x.x, x.x	x	x	x.x	x.x, x.x	x	x	x.x	xx, xx	x
	[PT 1]	x	x.x	x.x, x.x	x	x	x.x	x.x, x.x	x	x	x.x	xx, xx	x
	[PT 2]	x	x.x	x.x, x.x	x	x	x.x	x.x, x.x	x	x	x.x	xx, xx	x
[SOC 2]	Any PT	x	x.x	x.x, x.x	x	x	x.x	x.x, x.x	x	x	x.x	xx, xx	x
	[PT 1]	x	x.x	x.x, x.x	x	x	x.x	x.x, x.x	x	x	x.x	xx, xx	x
	[PT 2]	x	x.x	x.x, x.x	x	x	x.x	x.x, x.x	x	x	x.x	xx, xx	x
[Repeat for all SOC/PTs reported and for other challenge dose groups]													

Notes: N = Number of participants in the Safety population; n = Number of participants reporting each SOC/PT. A participant is only counted once per PT/time point. Confidence intervals for the probability of reporting a given event are calculated via the exact Clopper-Pearson method.

Table 60: Incidence of Unsolicited Adverse Events by MedDRA System Organ Class and Preferred Term, Maximum Severity, Relationship, and Challenge Dose Group

MedDRA System Organ Class	Preferred Term	Severity	10 ⁴ TCID ₅₀ Challenge Virus (N = X)				10 ⁴ TCID ₅₀ Challenge Virus (N = X)				10 ⁴ TCID ₅₀ Challenge Virus (N = X)				Sham Inoculum (N=X)				All Participants Receiving Active Challenge Virus (N=X)			
			Related		Not Related		Related		Not Related		Related		Not Related		Related		Not Related		Related		Not Related	
			n	%	n	%	n	%	n	%	n	%	n	%	n	%	n	%	n	%	n	%
Any SOC	Any PT	Any Severity	x	x.x	x	x.x	x	x.x	x	x.x	x	x.x	x	x.x	x	x.x	x	x.x	x	x.x	x	x.x
		Mild	x	x.x	x	x.x	x	x.x	x	x.x	x	x.x	x	x.x	x	x.x	x	x.x	x	x.x	x	x.x
		Moderate	x	x.x	x	x.x	x	x.x	x	x.x	x	x.x	x	x.x	x	x.x	x	x.x	x	x.x	x	x.x
		Severe	x	x.x	x	x.x	x	x.x	x	x.x	x	x.x	x	x.x	x	x.x	x	x.x	x	x.x	x	x.x
[SOC 1]	[PT 1]	Any Severity	x	x.x	x	x.x	x	x.x	x	x.x	x	x.x	x	x.x	x	x.x	x	x.x	x	x.x	x	x.x
		Mild	x	x.x	x	x.x	x	x.x	x	x.x	x	x.x	x	x.x	x	x.x	x	x.x	x	x.x	x	x.x
		Moderate	x	x.x	x	x.x	x	x.x	x	x.x	x	x.x	x	x.x	x	x.x	x	x.x	x	x.x	x	x.x
		Severe	x	x.x	x	x.x	x	x.x	x	x.x	x	x.x	x	x.x	x	x.x	x	x.x	x	x.x	x	x.x
	[PT 2]	Any Severity	x	x.x	x	x.x	x	x.x	x	x.x	x	x.x	x	x.x	x	x.x	x	x.x	x	x.x	x	x.x
		Mild	x	x.x	x	x.x	x	x.x	x	x.x	x	x.x	x	x.x	x	x.x	x	x.x	x	x.x	x	x.x
		Moderate	x	x.x	x	x.x	x	x.x	x	x.x	x	x.x	x	x.x	x	x.x	x	x.x	x	x.x	x	x.x
		Severe	x	x.x	x	x.x	x	x.x	x	x.x	x	x.x	x	x.x	x	x.x	x	x.x	x	x.x	x	x.x

Note: N = Number of participants in the Safety Population; n = Number of participants reporting each SOC/PT.

14.3.1.2 Solicited Adverse Events

This is just a placeholder for the CSR. No solicited AEs are collected for the 20-0005 study.

14.3.2 Listing of Deaths, Other Serious and Significant Adverse Events

Table 61: Listing of Serious Adverse Events

[Implementation Notes: If the event is ongoing (no stop date), indicate “ongoing” for the “Duration”. If more than one reason is selected for the reason reported as an SAE, list all reasons in the column, separated by commas. In the “If Not Related, Alternate Etiology” column, merge the 2 data fields for collecting alternate etiology, separate by a colon. If there are no comments for an event, populate ‘Comments’ row with ‘None’. Participant ID should be USUBJID (not PATID) for purposes of de-identification. Listing should be sorted by Challenge Dose Group, Participant ID, Associated with Dose No., and No. of Days Post Associated Dose.]

Adverse Event	No. of Days Post Challenge (Duration)	No. of Days Post Challenge the Event Became Serious	Reason Reported as an SAE	Severity	Relationship to Study Challenge	If Not Related, Alternative Etiology	Outcome	MedDRA System Organ Class	MedDRA Preferred Term
Participant ID: , Challenge Dose Group: , AE Number:									
Comments:									
Participant ID: , Challenge Dose Group: , AE Number:									
Comments:									

Table 62: Listing of Severe Influenza Complications Reported as Adverse Events

[Implementation Note: If the event is ongoing (no stop date), indicate “ongoing” in the “Duration” column. In the “If Not Related, Alternate Etiology” column, merge the 2 data fields for collecting alternate etiology, separate by a colon. If there are no comments for an event, populate ‘Comments’ row with ‘None’. Participant ID should be USUBJID (not PATID) for purposes of de-identification. Listing should be sorted by Challenge Dose Group, Participant ID, and No. of Days Post Challenge.]

Adverse Event	No. of Days Post Challenge (Duration)		Severity	Relationship to Study Challenge	If Not Related, Alternative Etiology	Outcome	MedDRA System Organ Class	MedDRA Preferred Term
Participant ID: , Challenge Dose Group: , AE Number:								
Comments:								
Participant ID: , Challenge Dose Group: , AE Number:								
Comments:								

